6.8. Evidence to support the failure of intramuscular injection in humans

In 1982, Cockshott et al. investigated the administration of IM injections into the upper outer quadrant of the buttock with CT. 213 patients were studied; the weight of participants was measured in 123 individuals - 60 women and 63 men. They compared skin to muscle measurements for a given weight. Women were found to have 2.5cm additional gluteal fat thickness for a given weight. It was estimated that more than 85% of males and 95% of females would have received their IM injections outside the gluteal muscle when using 3.5cm needles.⁶ The researchers also noted the presence of adipose calcification, suggesting previous 'IM injections' were possibly intra-lipomatous.⁶

Chan et al. 2006, observed a similar rate of failure of IM injections. Using CT imaging, they assessed upper outer quadrant gluteal IM injections in adults; only 32% were confirmed IM when using the standard 3cm 23G needle. There was significant difference between genders: 56% were correctly administered for males, compared with only 8% for females. Of the patients with a BMI of 25-29.9kg/m², 33% received IM injections. Above a BMI of 30kg/m², no patients received correct administration of IM injections.⁷

In 1975, Vukovich et al. noted significant PK variation between sexes in the absorption of cephadrine, specifically when administered in the gluteus maximus. In this study, 12 volunteers (six male, six female) received intramuscular injections in the deltoid, vastus lateralis, and gluteus maximus on different occasions. As demonstrated below in Figure 2, cephadrine serum concentrations were similar between sexes for the deltoid and vastus lateralis. However, when administered via the gluteus maximus, there was an unexplained significant difference in peak serum concentration. They did not comment on the possible reasons behind the difference.⁵⁴ Burbridge et al. 2005, reported similar significant differences in gluteal SC fat thickness between men and women, and suggested that using standard IM needles would result in 34% failure rate (14% males, 54.7% females).⁵⁵

[figure not shown]

Figure 2: Time to cMAX was 2.05 hrs (females) vs 0.63 hrs (males). Peak concentration was 4.30+/- 0.92µg/ml (females) vs 11.08 +/- 1.11 µg/ml (males), both statistically significant ($p < 0.05$). [Vukovich et al. (1975)]

6.9. Evidence that subcutaneous administration of medication has preferable characteristics

The above studies give support to the hypothesis that IM injections can be inadvertently administered to the SC/adipose tissue, possibly affecting the PK in certain individuals. Cephadrine, aspirin, and dapsone have all displayed PK differences which have been attributed to intra-adipose injections.^{56,57} The ideal characteristics of secondary prophylaxis is a long-acting depot of medication which is released in a predictable fashion to ensure that plasma levels remain above the MIC for *Streptococcus pyogenes*, the causative organism of ARF. The ability to extend the duration of therapy by altering route of administration has benefits for the patient (fewer injections), health care providers (human resources), and governments (financial savings).

Whilst there have been no human comparative studies with BPG investigating alternate routes, human studies involving other medications have revealed significant PK differences.^{54,58} In 2016, El Samad et al., compared the safety and tolerability of SC teicoplanin versus IV administration for the treatment of bone and joint infections. Thirty patients received a total of 1460 subcutaneous injections; doses of less than 800mg per dose were used and mixed into 50ml saline, then subsequently administered by gravity feed. It was noted that doses below 600mg were associated with fewer adverse reactions by SC injection, and no patient had a Grade 3 or above local reaction at any dose. The local reactions included: pain; swelling; erythema; warmth; itching; haematoma; and telangiectasia, with patients reporting greater pain at the end of the infusion compared to the start. Between 36-50% of participants experienced pain throughout the study, although it was not significant enough to withdraw from the study. The pharmacokinetics of teicoplanin were more favourable with the SC route of administration. A significantly higher C_{min} +6.51mg/L was noted, with SC vs IV ($p<0.001$).⁵⁸

6.10. Subcutaneous administration of antibiotics

Forestier et al. 2015, performed a national survey of The French Infectious Diseases Society (SPILF) and French Society of Geriatrics and Gerontology (SFGG) society networks. Of the 1800 surveys emailed to members, 382 responded from 160 hospitals across France. Three hundred and sixty-seven (96.1%) of respondents admitted to administering SC antibiotics. The most frequently prescribed subcutaneous antibiotic was ceftriaxone, being prescribed by all but one physician (n=366), with ertapenem (n=122, 33.2%), teicoplanin (n=144, 39.2%), aminoglycosides (n=129, 35.1%), amoxicillin (n=56, 15.3%), cefepime (n=9), imipenem (n=6), piperacillin-tazobactam (n=2), amoxicillin-clavulanic acid (n=2), ceftazidime (n=1), doripenem (n=1) also reported. The number of respondents who treated 6-10 or more patients per month via the SC route was 117 (31.8%). Two hundred and eighty-five respondents recorded their duration of SC therapy to be between 4-14 days; 69 respondents administered SC antibiotics for more than 14 days. Reasons for choosing SC therapy included IV/IM contraindicated, oral route contraindicated, avoiding oral polypharmacy, palliative care, and facilitating hospital discharge.⁸

Of the reasons for not prescribing SC antibiotics, the most frequent was the lack of PK data: 59.7% (n=219); 29.2% (n=107) cited the lack of marketing authorisation. Survey respondents did not comment on the adverse reaction rate or tolerance by patients, although given such a high number of clinicians admitting to using therapy for more than four days, it is suggestive that patient tolerance is acceptable.⁸

6.11. Pain of subcutaneous injections in humans

Berteau et al. 2015, investigated the effect of viscosity of injection in healthy adult volunteers. Using a comparative crossover design, they enrolled 24 adults (12 male, 12 female). They compared either low (0.02mL/s) or high (0.3mL/s) flow rates as well as viscosity of suspension of sodium chloride +/- hyaluronic acid at different viscosities: 1, 8-10, 15-20cP. They showed no difference in pain scoring due to injection rate ($p=0.79$), however, they showed a significant difference in pain scores dependent on the viscosity of the injection. Higher viscosity was associated with a lower pain score: visual analogue scale (VAS)=12.6mm vs 22.1mm. ($p=0.0002$). Volume of injection 2 or 3mL did not reveal a significant difference in pain ($p=0.89$).⁵⁹

6.12. Clinically significant reduction in pain

The VAS has been well validated as a method for determining differences in pain in clinical practice. Todd et al. 1996, demonstrated that a difference of 13mm (95% CI, 10-17mm) on a 100mm scale was a clinically significant change in pain severity.⁶⁰ This was validated in a larger study by Gallagher et al. 2001, in which they were able to replicate Todd et al. in 96 patients.⁶¹ Bijur et al., 2003, compared the VAS (0-100) to numerical reported scale (NRS) (0-10) and found no significant difference in the recorded pain levels.⁶² Cepeda et al. 2003, undertook a prospective study investigating what determined a clinically significant reduction in post-operative pain scores. They determined that a reduction in pain of 1.3 units in the NRS was clinically significant for those with moderate pain (NRS=6). With severe pain (NRS=8) the minimum clinically significant reduction in pain was 1.8 units.⁶³

6.13. Using ultrasound to determine the depth of injection and complications

The use of ultrasound (US) to determine and document the placement of both IM and SC injections is well described in the literature.^{64,65} The US findings of complications of IM and SC injections are described for other drugs but only case reports of rare complications after BPG are described.^{51,66,67} Confirmation of US-guided IM injection with MRI has demonstrated the reliability of US as a means of determining the depth of injection and avoidance of critical structures like blood vessels and nerves.⁶⁴ While the use of CT scan and MRI are more definitive in defining structures, their cost, associated risks, and utility at the bedside make them less applicable in the acute clinical setting.⁶⁸⁻⁷⁰

6.14. Potential risks and benefits of BPG to humans

6.14.1. Potential risks

AEs to Bicillin® L-A, are uncommon. Despite being the only current form of BPG licenced for use in Australia, there have been episodes of 'stockouts'.^{33,71} During these periods, a powdered form of BPG was used. A search of the Database of Adverse Event Notifications – from 1st January 1971 through to 18th February 2017 for all types of benzathine penicillin reveals only 22 case reports, 13 in which Bicillin® L-A was the only medication administered. There were no adverse reactions noted for the powdered BPG used during stockouts.⁴² Prior to 1995, Bicillin® L-A was only available in Australia in the 2.4 MIU unit prefilled syringe. It required clinicians to either use half of the dose or decant the Bicillin into a secondary syringe prior to administration.³³ Since 1995, there have been 11 adverse reactions reported to the TGA, seven in which Bicillin® L-A was the only administered medication. Of the seven, one reported a cardiac arrest, hypotonia, and seizure. One reported injection site reaction with abscess, four reported injection site reaction, one reported gait disturbance, three reported pyrexia, one reported otitis media, and one reported erythema, pain, rash, and swelling. From the period September 1997 through to May 2014, a total of 20,641 prescriptions were filled for Bicillin® L-A, representing a total of 206,410 doses prescribed.⁷¹ This corresponds to an almost zero absolute risk of reaction. BPG is a commonly used medication; the reported side effects/adverse drug reactions are mentioned in the product information sheet in Appendix 1.⁷²

Intramuscular injection is a frequently-used route of parenteral drug administration. In IM injections, the skin is broken, SC tissue is traversed, and medication injected into the muscle. IM injections have been shown to have increased absorption into systemic circulation compared to SC injections.⁷³ The most common side effects are pain, redness, and localised swelling. There is a small risk of: infection, damage to muscle, nerve, skin necrosis, inadvertent vascular damage/injection, anaphylactic reaction, and death. Most of the serious complications involving tissue necrosis will resolve with conservative management; a small percentage of severe cases may require medical procedures e.g. fasciotomy, if complicated by compartment syndrome.^{45,51} As with any drug, anaphylactic reactions can cause death in its most severe cases.

The risk of IV injection is present in SC injections, although the rates of inadvertent vascular damage are significantly lower than XX? owing to the reduced blood supply of SC tissue. SC granulomas are a common incidental finding on imaging; uncommonly, SC injections are thought to be responsible for the development of calcific granulomas and fat necrosis.⁴⁸ Kawai et al., 2014, reported on the rate of injection site reaction to depot SC injection of leuprorelin acetate. Over a 5-year period at Tokai University Hospital, they identified 13 out of 335 (3.88%) of patients had a reaction to the depot injection. Eleven cases of SC induration were reported, as well as one ulceration and one SC ulceration and mass. Additionally, they examined case reports from 1999 onwards and identified 37 cases of SC granuloma formation. They noted that almost half of the granulomas spontaneously resolved (15/37).⁷⁴

6.14.2. Known / potential benefits

The participants will not benefit directly from this study and most risks are transient in nature (pain, redness). The outcomes of the study will benefit those required to have secondary prophylaxis for ARF and RHD. Good adherence to secondary prophylaxis with BPG is effective in reducing recurrence and progression of ARF to RHD.²³ Children often have significant pain associated with their injection, and the pain and fear of pain is frequently cited as a reason for poor adherence to the 4-weekly injections.^{5,17,30} This cohort of individuals are the ones who will directly benefit from this study. Bicillin® L-A has a narrow spectrum of activity, which is beneficial for antimicrobial resistance. GAS has remained exquisitely sensitive to penicillin, with no documented isolates of *Strep pyogenes* resistant to penicillin identified.⁷⁵ It does, however, display resistance to other classes of antibiotics e.g. macrolides and lincomycin.²⁶ Rates of resistance to macrolide antibiotics vary according to local factors and can rapidly change.²⁵

The people to benefit from this trial are those who also suffer from the other diseases treated by BPG: pharyngitis, cellulitis, syphilis yaws, bejel, and pinta. Of those to benefit the most are individuals who require repeated BPG injections, with an estimated 33.4 million people living with RHD worldwide and an annual 319,400 deaths due to RHD.² This alone is sufficient reason to undertake this study. Additionally, there are approximately 5.6 million new cases each year of syphilis and an estimate prevalence of 0.5% amongst the 15-49 year age group, giving a worldwide prevalence of more than 18 million.¹⁵ Approximately 162 million individuals are estimated to be suffering from impetigo at any one time.¹⁴ There are an estimated 616 million cases of GAS pharyngitis per year.¹⁹ BPG is currently listed as an essential medication by the WHO; given its widespread use, any individual who needs treatment may benefit from an improved delivery method. Whilst the Bicillin® L-A is used in high resource countries owing to the cost and cold chain dependence, the results of this study will provide valuable information for future planned BPG reformulation and RHD control programs in other countries.

Table 2: Estimated number of potential beneficiaries of this BPG study

Disease	Estimated Burden
ARF/RHD	33.4 million
Pharyngitis	616 million/yr
Impetigo	162 million cases
Syphilis	18 million

This study will determine if Bicillin® L-A, when given at an equivalent dose, is tolerated via SC injection. This information will also provide further background knowledge regarding potential future reformulation of BPG.

6.15. Name and description of the intervention or product(s) used in this trial

The investigational medical product (IMP) for this trial is Bicillin® L-A 1016.6mg (1.2 MIU) in 2.3ml. This product is registered with the Australian Therapeutics Goods Administration (TGA AUST R 147169).

7. TRIAL DESIGN

7.1. Description

This is a phase 1, investigator-initiated singled-blinded, longitudinal two by two crossover clinical trial to assess the pharmacokinetics of Bicillin® L-A administered to healthy adult volunteers. Participants will be recruited using the Linear Clinical Research volunteer database. They will undergo screening to ensure that they fit the inclusion criteria detailed in section 8. Baseline physical measurements and blood sampling will occur as outlined in section 9. Randomisation and blinding will occur once the participant has satisfied the inclusion criteria as outlined in section 10.

Participants will receive two injections in total. It will be a randomized two by two longitudinal crossover trial with a washout period of 10 weeks between administration periods. The number of participants in the study will be 15.

Participants will be randomised to either receive:

- (a) Group A: IM injection → washout → SC injection, OR
- (b) Group B: SC injection → washout → IM injection

Table 3: Representation of the study periods

	Duration (weeks)	Group A	Group B
Administration Period 1	6	IM	SC
Washout period	4	Washout	Washout
Administration Period 2	6	SC	IM
Follow up (telephone)	2	Follow up	Follow up

7.2. Hypotheses

Primary hypothesis:

1. Administering Bicillin® L-A via the SC route will result in a clinically significant reduction in the rate of absorption (K_a) compared with IM absorption. This will result in clinically relevant prolongation of the duration that penicillin concentrations remain above the minimum inhibitory concentration (0.02mg/ml) for *Streptococcus pyogenes*.

Secondary hypothesis:

1. Administering Bicillin® L-A via the SC route will result in improved or comparable tolerability compared to the current recommended IM route.

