2. STUDY SYNOPSIS

TITLE	Pharmacokinetics of Intramuscular Versus Subcutaneous Administration of Benzathine Penicillin G (Bicillin® L-A)
OBJECTIVES	
Primary Aim:
 
 To compare the pharmacokinetics, in particular, the rate of absorption of Bicillin® L-A administered by the subcutaneous route and the intramuscular route in healthy adults 
Secondary aims:
 
 To measure the pain experienced by participants administered Bicillin® L-A by the subcutaneous route compared to the intramuscular route To measure the frequency, types, and severity of adverse events related to Bicillin® L-A administered by the subcutaneous route compared to the intramuscular route
DESIGN	A single-blinded study in 2x2 crossover using two doses of Bicillin® L-A administered by the subcutaneous and intramuscular route with a 10-week wash-out period between doses. Serum penicillin levels and pain scores just prior to injection and at pre-determined intervals for six weeks following each injection will be collected. An ultrasound scan will be used to guide and confirm injection site and document location of medication bolus on injection day and local changes at injection sites at four weeks after injection.
OUTCOMES	
Primary outcome measure:
 
 The rate of absorption of Bicillin® L-A administered subcutaneously and intramuscularly 
Secondary measures:
 
 Time above the minimum inhibitory concentration (0.02mg/mL) for Streptococcus pyogenes Pain scores associated with receiving Bicillin® L-A administered subcutaneously and intramuscularly Type, number, and severity of adverse events following subcutaneous compared to intramuscular administration of Bicillin® L-A Type and number of ultrasound-detected local changes following subcutaneous compared to intramuscular administration of Bicillin® L-A
STUDY DURATION	Six months (each participant will be in the study for 18 weeks)

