In 2011, Broderick et al. conducted a PK study whereby BPG was administered to healthy military recruits, and noted that levels were lower than expected. In total, 329 adult males were

administered 1.2MIU of BPG, and blood samples were taken for PK analysis. Nine days after BPG delivery, 50% of the cohort had a concentration of penicillin G less than 0.02µg/mL, the accepted standard for protection against GAS.⁹ The researchers did not draw any conclusions as to the possible causes of this variation.

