7.4. Secondary endpoints

- (a) Pain scores related to administration of Bicillin® L-A for the SC and IM routes.
- (b) Defined AEs related to SC and IM routes of administration of Bicillin® L-A.
- (c) Time above the MIC for Bicillin® L-A administered via the SC and IM routes.

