12.2. Sample size and power calculation

Sample size was calculated based on a clinically significant and likely reduction in the primary outcome measure, namely the rate of absorption (K_a). This was set at around 40% for the following reasons: i) based on simulation data for children this would increase the median time above 0.02mg/L by around one week from 15 to 22 days and ii) animal studies comparing IM to SC dosing observed this difference (Ranheim et al⁴⁴).

Power calculations were performed within NONMEM using a combination of local data in children and a published population PK model of IM benzylpenicillin in adults (Neely et al⁸²) to perform Monte-Carlo mapped power implemented via Perl-Speaks-NONMEM. The simulations assumed a slower absorption with SC dosing using the crossover design and the planned sampling schedule. There was over 90% power with an alpha of 0.05 (significance level of 5%) to detect a difference of 40% with 11 participants. There was also around 80% power to detect a 30% difference with 14 participants.

To account for possible loss to follow-up and unpaired data, a target of 15 participants was set.

[figure not shown]

Figure 3: Power calculations for study recruitment

Rationale of sample size for pain assessment:

Using a t-test with matched pairs, discrimination of 2 points with a SD of 1.7 should be attainable. Studies have shown that a reduction of pain by 30% is considered clinically significant. Therefore, to determine a difference in pain between the two routes, we considered a 30% difference to also be significant. We assumed a correlation between groups of 0.3; hence, n=15 results in power to discriminate of 94.6%; n=10 will result in power of 79.8% and n=12, 87.9%.

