Intramuscular benzathine benzylpenicillin is absorbed very slowly into the bloodstream from the intramuscular site and converted by hydrolysis to benzylpenicillin. This combination of hydrolysis and slow absorption results in blood serum levels much lower but much more prolonged than other parenteral penicillins.

Intramuscular administration of 225 mg of benzathine benzylpenicillin in adults results in blood levels of 22.5 to 37.5 nanogram per mL, which are maintained for 4 to 5 days. Similar blood levels may persist for 10 days following administration of 450 mg and for 14 days following administration of 900 mg. Blood concentrations of 2.25 nanogram per mL may still be detectable 4 weeks following administration of 900 mg.

Distribution

Approximately 60% of benzylpenicillin is bound to serum protein. The drug is distributed throughout the body tissues in widely varying amounts. Highest levels are found in the kidneys with lesser amounts in the liver, skin and intestines. Benzylpenicillin penetrates into all other tissues and the spinal fluid to a lesser degree.

Excretion

With normal kidney function, the drug is excreted rapidly by tubular excretion.

In neonates and young infants and in individuals with impaired kidney function, excretion is considerably delayed.

INDICATIONS

Intramuscular benzathine benzylpenicillin is indicated in the treatment of infections due to penicillin-sensitive micro-organisms that are susceptible to the low and very prolonged serum levels common to this particular dosage form. Therapy should be guided by bacteriological studies (including sensitivity tests) and by clinical response.

The following infections will usually respond to adequate dosage of intramuscular benzathine benzylpenicillin:

Streptococcal infections (Group A - without bacteraemia). Mild-to-moderate infections of the upper respiratory tract (eg., pharyngitis).

Venereal infections - Syphilis, yaws, bejel and pinta.

Medical conditions in which benzathine benzylpenicillin therapy is indicated as prophylaxis:

Rheumatic fever and/or chorea - Prophylaxis with benzathine benzylpenicillin has proven effective in preventing recurrence of these conditions. It has also been used as follow-up prophylactic therapy for rheumatic heart disease and acute glomerulonephritis.

CONTRAINDICATIONS

Previous hypersensitivity reaction to any of the penicillins.

PRECAUTIONS

Allergic reactions

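### The MIC threshold is written as 0.02 mg/mL in the synopsis outcome and the primary hypothesis, 1,000 times the 0.02 mg/L used in the background and sample-size rationale

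*Protocol*

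**What the plan says.** The protocol refers to one threshold, for penicillin against *Streptococcus pyogenes* (group A streptococcus), in five places.

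- **Synopsis, secondary measure 1:** "Time above the minimum inhibitory concentration (0.02mg/mL) for" this organism.
- **Section 7.2, second sentence of the primary hypothesis:** slower subcutaneous absorption is expected to lengthen the time that "penicillin concentrations remain above the minimum inhibitory concentration (0.02mg/ml").
- **Section 7.4(c), secondary endpoints:** "Time above the MIC for Bicillin® L-A administered via the SC and IM routes", with no number.
- **Section 6.2, background:** in a study of 329 adult male recruits given 1.2 MIU, half of the cohort at nine days "had a concentration of penicillin G less than 0.02µg/mL, the accepted standard for protection against GAS".
- **Section 12.2, sample-size rationale:** for a reduction of about 40% in the absorption rate Ka, and on simulation data for children, "this would increase the median time above 0.02mg/L by around one week from 15 to 22 days".

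The product information in Appendix 1 adds the scale of concentrations after intramuscular injection. In adults, 225 mg "results in blood levels of 22.5 to 37.5 nanogram per mL" for 4 to 5 days. Similar levels may last 14 days after 900 mg, and 2.25 ng/mL may still be detectable at four weeks. Section 10.4.2 repeats the four-week figure for the 1,200,000-unit dose.

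**The concern.** The threshold defines the derived variable: time above MIC is the time that a concentration curve spends above it. The two places that state the outcome and the hypothesis use milligrams per millilitre. The lower value appears only in a literature summary and in a power rationale. Section 7.4(c) cannot settle the matter because it gives no value, so someone specifying the endpoint would naturally take the figure from the synopsis or from section 7.2.

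At stake are secondary endpoint (c) and the second sentence of the primary hypothesis. That sentence gives the Ka comparison its clinical meaning, since section 12.2 justifies the target reduction in Ka partly by the gain in time above 0.02 mg/L.

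**Working it through.** **Step 1. Put the stated thresholds in one unit (ng/mL).**

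| Place | As written | In ng/mL |
|---|---|---|
| Synopsis outcome | 0.02 mg/mL | 0.02 × 1,000,000 = 20,000 |
| Section 7.2 | 0.02 mg/mL | 20,000 |
| Section 6.2 | 0.02 µg/mL | 0.02 × 1,000 = 20 |
| Section 12.2 | 0.02 mg/L | 0.02 × 1,000,000 / 1,000 = 20 |

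Sections 6.2 and 12.2 agree. The synopsis and section 7.2 are higher by 20,000 / 20 = 1,000.

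**Step 2. Compare both thresholds with the product-information levels.**

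| Level (ng/mL) | 20,000 / level | Level / 20 |
|---|---|---|
| 37.5 | 533 | 1.9 |
| 22.5 | 889 | 1.1 |
| 2.25 (four weeks) | 8,889 | 0.11 |

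At 20 ng/mL, the sustained levels lie just above the threshold and the four-week level lies below it, so a curve crosses it within the sampling period and yields a number of days. The recruit study in section 6.2 supports this in adult men at the trial dose: half were below 20 ng/mL at day nine. At 20,000 ng/mL, all these levels are several hundred to several thousand times too low.

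**Step 3. Could an unreported early peak exceed 20,000 ng/mL?** The product-information levels are sustained levels, not peaks. A peak 100 times higher would be 2,250 to 3,750 ng/mL, still under 20,000. Reaching the threshold would take a peak 533 to 889 times the sustained level.

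**Step 4. A rough check from the figures in section 12.2.** The protocol's NONMEM simulation cannot be rerun from the document. As a simplification, assume absorption-limited decay, C(t) = C0·exp(−Ka·t), with C0 proportional to Ka. For threshold M, the time above it is T = ln(C0/M)/Ka. Cutting Ka by 40% multiplies both Ka and C0 by 0.6, so

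Ka = −ln(0.6) / (T1 − 0.6·T2).

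With T1 = 15 and T2 = 22 days, Ka = 0.511 / (15 − 13.2) = 0.284 per day.

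The starting level is 0.02·exp(0.284 × 15) = 1.41 mg/L for intramuscular dosing and 0.6 × 1.41 = 0.85 mg/L for the slower route. Both are below 20 mg/L, so the time above 0.02 mg/mL is 0 days on each.

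The starting level is sensitive to rounding of the longer time. The intramuscular value is 0.49 mg/L if T2 is 21 days and 11.9 mg/L if it is 23. All three are below 20 mg/L. This check rests on medians simulated for children, so it supports the order of magnitude only.

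**The case against.** The strongest reply is that this is a recoverable slip. The lower value stands twice in the same protocol, once described as the accepted standard. A pharmacokineticist would notice a column of zeros. Time above MIC is derived from measured concentrations, so it can be recomputed with no data lost, and the SAP, which is not at hand, may already use the lower value. All of this limits the harm. It does not correct the outcome and hypothesis as stated, and an SAP using 0.02 mg/L would itself disagree with them.

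A lost µ sign in the electronic text is conceivable but unlikely: µ appears correctly in section 6.2, and the milligram-per-millilitre form occurs in two separate places.

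Three stronger readings are tempting, and the documents do not support them.

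- **A reader might infer that the primary analysis is compromised.** The primary endpoint is Ka (section 7.3), which uses no MIC. The power calculation is for a difference in Ka, and its rationale already uses 0.02 mg/L.
- **A reader might infer that zero days is proven for every participant.** The protocol gives no peak concentration for this dose and no human subcutaneous levels, and the 22.5 to 37.5 ng/mL range is quoted for 225 mg. Slower subcutaneous absorption would imply a lower peak, but that is the hypothesis, not an observation.
- **A reader might infer that a planned result of 15 against 22 days would be lost.** Those figures come from a simulation in children. The trial enrols men aged 18 to 65, and the recruit study suggests a median nearer nine days after intramuscular dosing.

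**Conclusion.** The point holds as an internal contradiction in units. The written threshold is exactly 1,000 times the value in the background and sample-size rationale, and it stands where the outcome and hypothesis are stated. This needs no assumption beyond unit conversion.

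That time above MIC would be zero on both routes if the text were applied literally is very probable rather than certain. It rests on the product-information levels lying 533 to 889 times below 20,000 ng/mL, and on early peaks not closing a gap of that size. In that case, secondary endpoint (c) and the time-above-MIC part of the hypothesis would be uninformative until recomputed. The intended value is clear, because only 20 ng/mL agrees with the protocol's own literature summary, its simulation rationale and the appended concentrations.

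**What to change.** Change the unit to 0.02 mg/L (= 0.02 µg/mL) in the synopsis outcome list and in section 7.2. Write the same value into section 7.4(c), so that the endpoint uses the threshold of the sample-size rationale, and carry it into the SAP.

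The cost is two unit corrections and one added value in the next protocol amendment. This is an analysis threshold, so sampling, dosing, sample size and the primary analysis do not change.
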